1.0 INTRODUCTION AND BACKGROUND

1.1 Common Warts of Hand and Fingers

Non-genital warts (*verruca vulgaris*) are an extremely common, benign, and usually a self-limited skin disease. Infection of epidermal cells with the human papillomavirus (HPV) results in cell proliferation and a thickened, round, raised papule on the skin ranging in size from a pinhead to 10 mm. The appearance of warts is determined by the type of virus and the location of the infection. There are several reasons why some individuals are affected by warts, and others remain trouble free. These include: the type and strength of the viral strain, the health of the exposed person, and the strength of an individual's immune response. Any area of skin can be infected, but the most common sites are the hands and feet. Common warts are most often seen on the hands and present as skin-colored papules with a rough 'verrucous' surface.

1.2 Current Care

Current treatments for common warts involve destruction of the infected cells either chemically or physically and treatment depends on the size, location, number, type, age of the patient, risk of scarring and patients' commitment to the therapy. The clinical management of these warts is challenging, and no current treatment is singularly effective, especially against warts that are recalcitrant. These include non-surgical, pharmacologic, and surgical treatment modalities: topical peeling methods like salicylic acid; immune modulators using contact immunotherapies; intralesional candida antigen or bleomycin; cryotherapy; duct tape occlusion; photodynamic treatment; pulsed dye laser; and general surgical procedures.

1.3 Non-Surgical Approach

Chemical Destruction:

Salicylic Acid

The use of salicylic acid is one of the two most commonly used treatments for warts. Dermatologists prescribe chemical destruction treatments where patients apply an over-the-counter preparation, usually less than 17% salicylic acid or prescription salicylic acid containing up to 70% salicylic acid at home every day. Treatment response rates of 40-84% with an average of 61% have been reported as an effective therapy for non-genital cutaneous warts.¹ Minor skin irritation was reported occasionally in some of the other trials, but generally there were no major harmful effects of topical salicylic acid.² A systematic review of local treatments of cutaneous warts by Mitsuishi et al., found evidence that topical treatments with salicylic acid have a therapeutic effect, with a cure rate of 75 percent compared with 34-48 percent in placebo controls.^{1,3} Other agents used for chemical destruction are monochloracetic acid, dichloracetic acid, trichloroacetic acid, silver nitrate, glycolic acid and 80% phenol in solution. Complications associated with using chemicals include pain, hyperpigmentation, hypopigmentation, burning sensation and erythema.⁴

Cantharidin

Cantharidin is used as an agent in the clinic by "painting" the wart causing oxidative stress by inhibiting phosphatases 1 and 2A that damages both DNA single- and double-strand breaks and triggers p53 dependent apoptosis.⁴ Cantharidin causes a blister to form under the wart. In a week or so, the patient returns to the office and the dermatologist clips away the dead wart.

Immune Modulators

1.4 Surgical Approach

Electrosurgery and Curettage

Electrosurgery (burning) is an available treatment for common warts, filiform warts, and foot warts. Curettage involves scraping off (curetting) the wart with a sharp knife or small, spoon-shaped tool. These two procedures often are used together. The dermatologist may remove the wart by scraping it off before or after electrosurgery.

Excision

The wart may be cut off or surgically excised in combination to using other applications previously mentioned.

1.5 Alternative Approach

CellFX® System

The CellFX System is intended to clear the skin of benign, undesired skin lesions as an alternative to surgery and other more destructive methods for removing non-neoplastic benign lesions. The CellFX System utilizes non-thermal, localized delivery of a timed series of low energy, nanosecond electrical pulses that can trigger regulated cell death. The non-thermal effect on tissue takes place in a very shallow depth of skin directly below the sterile treatment tip. Histology of skin treated with CellFX has demonstrated selective non-thermal effects on cellular structures, including melanocytes, epidermal cells, and sebaceous glands, with no apparent damage to the adjacent acellular dermis.

The device delivers less energy to tissue, but none of these emit thermal energy unlike laser, electro-surgery, or electro-cautery equipment.

PRIOR CLINICAL STUDIES SUMMARY

Twelve (12) clinical studies have been or are currently being conducted using IRB approved non-significant risk protocols and consent with the Nano-Pulse Stimulation (NPS) device. A combined total of approximately 3,125 NPS application cycles have been delivered to over 680 adult subjects. Anatomic locations where NPS has been used include the face, abdomen, truncal, back, arms, legs, hands, and feet. Discomfort in all protocols was managed with localized injected buffered Lidocaine with or without epinephrine. Side effects consisted of relatively minor reactions consistent with routine wound healing. No device or procedure complications and no serious related adverse events were reported. Only minor expected adverse skin effects have been reported and they were resolved within days of the procedure.

Previous Wart Studies Using CellFX System

Nineteen (19) adult subjects were enrolled with the requirement of having a minimum of 2 and up to 5 non-genital, off-face cutaneous warts with one of the warts designated as a sham control. Subjects received an initial NPS treatment and returned for follow-up evaluations at 7-, 30- and 60 days post-last treatment. Each wart was evaluated for size reduction at 30-days for eligibility for retreatment and at 60-days post-last NPS session using a 5-point size scale. At the end of the study, all subjects were asked about their satisfaction with each treated lesion clearance based on a 5-point scale from 1 equaling highly dissatisfied and 5 being satisfied.⁷

Six (6) of the nineteen subjects were male (32%) and 13 were female (68%). Subjects ranged in age from 23 to 71, with an average age of 47. Fitzpatrick skin types were distributed across Type I (5%), Type II (58%), and Type III (37%). Fifty-two percent (52%) of warts were recalcitrant with 69% common warts located on the hands, fingers, and shoulders and the remaining 31% plantar warts. A total of 58 warts were enrolled in the study, 40 treated and 18 controls including one subject having all warts treated without a sham control. Two subjects withdrew early from the study giving a total per protocol population cohort of 37 treated and 16 control warts for evaluating wart reduction and clearance rates at 60-days post-treatment. Fifty-one percent (51%) of treated warts (19/37) received two treatments and 65% (n=20 common and 4 plantar) showed greater than 50% reduction in size with 51% (n=19) rated completely clear at 60-days post-treatment. Three (3) out of 16 sham control warts (18.8%) showed 100% reduction in size, suggesting a possible immune response involved with use of NPS. There were no observations of hypopigmentation and only 3 cases of hyperpigmentation at 60 days. No serious adverse events were reported, however in a few cases local bruising or formation of blood blisters post-treatment were noted that resolved by Day 7 or Day 30. Based on these initial results of achieving a high rate of wart size reduction, inclusive of recalcitrant warts, and with a single NPS session, a pivotal clinical study was initiated to further evaluate energy parameter settings of NPS technology for optimal clinical outcome.⁷

The IRB-approved NSR Protocol# NP-WP-010 pivotal study was designed as a prospective, non-randomized, multicenter study to evaluate the safety and efficacy of the CellFX System with expanding the number of clinical sites to 5 and using larger tip sizes as well as increasing the number of retreatments for investigators to clear cutaneous non-genital warts. Similar to the feasibility study each subject had to have a minimum of 2 warts with one wart serving as the subject's internal control. Additionally, at the 30-day, 60-day and 90-day visits the Investigator had the option to retreat any previously treated wart and were followed for 30 and 60-days post last CellFX treatment (NCT04554394).

A total of 62 subjects and 267 study warts (195 treated and 62 sham controls) with an average of 4.1 warts per subject were enrolled and evaluated at 60-days post last treatment. Forty-two subjects were female (68%) and 20 were male (32%) with an average age of 47.3. Fitzpatrick skin types were distributed across Type I (5%), Type II (44%), Type III (32%) and Type IV (19%). More than 70% of all treated warts were located on the hands, knee, ankle, arm, leg, neck, and torso while the remaining 30% were plantar warts. Pre-treatment with intralesional injection of sodium bicarbonate buffered 1-2% lidocaine with 1:100,000 epinephrine was used to control pain (mean, 1.0ml). Subjects reported a median 4.0 at the time of treatment based on a 11-point visual pain scale, with 47.8% reporting a score of 0 or 1.

Overall efficacy at 60-days post-last treatment showing greater than 90% reduction in size was observed in 77.4% of common (72/93) and 43.8% of plantar warts (14/32). Single treatment efficacy at 60-days post-last treatment showed 81% (51/63) in patients with common warts and 31.6% (6/19) with plantar warts. Subject satisfaction at the end of study was reported in 73.7% (98/133) of subjects being satisfied with final results. As previously described in the wart feasibility study, there were 11 sham control warts (17.7%) showing 100% reduction in size. A total of 31 cases of transient hyperpigmentation (22.8%); 61% mild, 35% moderate, 3% mod/severe and 8 observations of hypopigmentation (5.9%) were observed at 60-days post-last treatment. No serious adverse events were reported however, 9 treatment-related adverse events (6 mild and 3 moderate severity) of transient pain, numbness, or infection were reported. These AEs occurred on the hands (n=5) or plantar area (n=4) and all were resolved with no associated sequela.⁸

This new wart comparison study under Protocol NP-WC-015 will evaluate safety and efficacy using the CellFX System with pre-defined treatment energy profiles for all primary and secondary treatments based on the tip size. The comparator group will be treated with cryosurgery with liquid nitrogen for the treatment of warts.

1.6 Study Rationale

The rationale for this IDE study is to compare the safety and effectiveness of the CellFX System to the comparator group, Cutaneous Cryosurgery performed with direct application with liquid nitrogen for the treatment of cutaneous, non-genital common warts in healthy adult subjects.

2.0 STUDY DEVICE DESCRIPTION

The study device being evaluated is the Pulse Bioscience CellFX® System.

2.1 Pulse Bioscience CellFX® System

The CellFX System consists of an electrical pulse console (similar to devices used to electro-coagulate tissue) combined with a handpiece which is held by the clinician during application of pulses to the skin surface. The handpiece is coupled to a sterile, single patient-use treatment tip.

Once the electrical pulse console is turned on and a predetermined treatment energy setting is selected, a sequence of pre-programmed electrical pulses is administered to an area of skin directly beneath the treatment tip. A common commercially available sterile contact gel may be applied to the skin or treatment tip surface to ensure good electrical contact to the tissue. The three system components are as follows, shown in **Figures 1-3**.

1. CellFX Console including a built-in touch screen for setting selection.
2. CellFX Handpiece (re-usable)
3. Sterile Single Patient-Use CellFX Tip (multiple different tip sizes available)

Figure 1: CellFX Console

Figure 2: CellFX Handpiece

[figure not shown]

Figure 3: CellFX Treatment Tips

2.2 Proposed Indication for Use

The Pulse Biosciences' CellFX System is investigational in the U.S. and the system is indicated for dermatologic procedures requiring ablation and resurfacing of the skin including the treatment of common warts.

2.3 Cryosurgical System

The comparator device that will be used in this study is the standard of care procedure using liquid nitrogen to treat warts. The liquid nitrogen procedure uses a single freeze thaw cycle, with warts placed in contact with a metal probe (spray tip) held at liquid nitrogen temperature until a 2 to 3 mm halo is visible around each wart. All physicians are required to use the same Cryosurgical System.

3.0 PROTOCOL

3.1 Study Objectives

The primary objective of this study is to compare the safety and effectiveness of the CellFX System to Cryosurgery for the clearance of cutaneous non-genital common warts on all areas of the body, excluding the scalp, nose, within the orbital region of the face, plantar or periungual area in healthy adult subjects.

The following objectives are to evaluate the overall response to CellFX and Cryosurgery:

- Wart response after treatment vs. the pre-treated appearance of the same lesion
- Wart response at various points in time over several weeks following the initial treatments vs. the same pre-treated wart
- Overall wart clearance (generally accepted as complete clearance of warts from the treated area)
- Comparisons of reduction from baseline in wart size of treated warts
- Document the condition of skin in the treatment areas over the course of various time periods post-initial CellFX and Cryosurgery, and
- Document all safety related issues that may be considered as adverse side effects or serious adverse events

3.2 Study Design

This study is designed as a prospective, multicenter, single-blinded, randomized comparison IDE study between CellFX System and Cryosurgery. The Principal Investigator will select a sub-investigator to be the blinded investigator to classify the healing characteristics and wart clearance and/or reduction assessment of each subject's selected warts at baseline, post treatment and at 7-days, 30-days, 60-days, and 90-days following the last CellFX treatment or Cryosurgical procedure. This sub investigator will be blinded to the treatment assignment. The subject may not be blinded to the treatment assignment. The Principal Investigator can choose to be the blinded investigator and select a sub investigator to be the treating investigator.

Eligible subjects with a minimum of 2 and up to 8 warts meeting the inclusion and exclusion criteria will be enrolled. If the subject has more than 8 warts, the subject is excluded from the study. Warts may be present anywhere on the face except the scalp, nose and within the orbital region of the face. Plantar warts are also excluded. Subjects will be randomized to receive either a CellFX treatment or Cryosurgery. Selected warts for each treatment modality must be clearly separated in distance from each other so that wart treatment and side effects can be assessed by the blinded site investigator.

All eligible warts will receive at least one CellFX or Cryosurgical treatment. Each subject will be evaluated by the blinded site investigator at 7-days, 30-days, 60-days, and 90-days post-initial CellFX and Cryosurgical treatments. At the 30-day or 60-day follow-up visit, if any wart is classified as “not resolved”, the wart must receive an additional treatment. In case of a second or third retreatment, the subject will be evaluated by the blinded site investigator at 30-days, 60-days, and 90-days post-retreatment. Photography of the warts will be captured along with the blinded site investigator assessments at all visits.

Numbness (diminished/ altered sensation) Assessment: The treating investigator will conduct a “light touch” exam to all treated areas at baseline, 7 days and 30 days post initial treatment and 30 days post retreatment(s). Light touch is tested with a cotton wisp, feather, and/or even light finger touch. The subject will be asked how one area feels compared to another.

Note 1:

Eligible warts that should be treated and do not receive a retreatment will be considered a protocol deviation. The reason(s) for not receiving an additional treatment will be collected on the electronic case report form (eCRF). These subjects will remain in the study and will be included in the ITT population.

Additionally, subjects can only receive two additional treatments or up to a maximum of three CellFX or Cryosurgical procedures.

Non-Treated Wart Criteria: Data will be collected on ineligible or non-treated warts for all enrolled subjects. Non-treated warts are defined as flat, periungual, subungual, mosaic, plantar, filiform and/or common warts that are excluded due to anatomic location. Photography of the non-treated warts will be captured at baseline and the last study visit.

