- Photographic images of all treated warts will be taken with pre- and post-wart markings
- All warts will be clinically assessed by the blinded site investigator (wart healing characteristics, wart clearance and wart reduction assessments)
- Assessment of numbness in the treated area will be performed by the treating investigator

- If any wart is classified as “not resolved”, a second treatment with CellFX or Cryosurgery will be performed to the previously treated wart(s)

In case of a second CellFX or Cryosurgical treatment is required:

- Local anesthesia/numbing will be applied to each wart designated for a CellFX retreatment
- Each wart designated for a CellFX retreatment will be treated using pre-determined energy settings
- Each wart designated for Cryosurgical retreatment will be performed as outlined in protocol **Section 3.5**
- The subject will be asked to rate his/her pain immediately after each wart treated with CellFX and/or Cryosurgery by using a numerical rating score
- The subjects will be asked whether they felt muscle twitching immediately after each lesion treated with CellFX
- Immediately post-procedure, a wart healing characteristics assessment will be performed by the blinded site investigator
- Photographic images of all retreated warts will be taken post-treatment
- A light bandage and/or any physician recommended dressing may be applied before the subject leaves the clinic
- Any adverse events will be identified and documented with a live assessment by the blinded site investigator

4.8 60-Day Follow-up Visit (CellFX/Cryosurgical Treatment #3, if required)

- Photographic images all treated warts will be taken with pre- and post-wart markings
- All warts will be clinically assessed by the blinded site investigator (wart healing characteristics, wart clearances and wart reduction assessments)
- Assessment of numbness in the treated area will be performed by the treating investigator (only for those subjects who received a retreatment at the 30-day follow-up visit)

- If any wart is classified as “not resolved”, a third treatment with CellFX or Cryosurgery will be performed to the previously treated wart(s)

In case of a third CellFX or Cryosurgical treatment is required:

- Local anesthesia/numbing will be applied to each wart designated for a CellFX retreatment
- Each wart designated for a CellFX retreatment will be treated using pre-determined energy settings

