6.4 Populations for Analyses

The primary analysis dataset for study outcomes will be the intent-to-treat (ITT) population wherein data from all randomized warts will be analyzed based on the intended randomization assignment. The intent of this protocol is to apply up to 3 sessions of each treatment, but no warts will be

excluded from the ITT population based on the number of treatments actually received. The primary efficacy analysis will be performed using the ITT population. A modified intent-to-treat population will include all warts that received at least one treatment, and the primary efficacy analysis will also be calculated for this population for comparison. The modified ITT population will be the analysis population for the primary safety endpoint.

Study outcomes will also be analyzed using a per-protocol (PP) population. The PP population includes all subjects who had no pre-specified inclusion and exclusion violations, received either CellFX or Cryosurgery, and repeated the treatments per protocol for any warts classified as “not resolved” at the 30-day and/or 60-day visit.

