6.5 Sub-Group Analyses

Primary and secondary endpoints will be evaluated for the ITT and PP populations, as well as analyzed in strata based on the following sub-groups:

- Number of treated warts (2 to 4 or 5-8)
- Age
- Prior treatment for treated warts
- Gender
- Clinical Site
- Treatment Energy Level
- Size of CellFX Treatment Tip
- Total Energy Density
- Number of Treatments

These analyses are meant to assess consistency of treatment effects only, and this study is not powered for inference within subgroups.

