10.3.2.1 Stopping Rules

- a) Full dermal thickness ulcer in any subject, of any duration;
- b) Any depth ulcer or erosion lasting ≥ 30 days, in more than 2 of the first 20 subjects treated with CellFX or more than 10% of subjects treated after the first 20 subjects; and
- c) Scab or crust that is so severe at the 30 day visit that it would preclude additional treatment that day, in more than 2 of the first 20 subjects treated with CellFX or more than 10% of subjects treated after the first 20 subjects.

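### Mandatory retreatment conflicts with stopping rule (c), and a retreatment withheld for a severe scab removes the subject from the supportive per-protocol safety analysis

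*Combined protocol and SAP*

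**What the plan says.** Section 3.2 sets one criterion for retreatment at the 30-day and 60-day visits. If a wart is classed as unresolved, "the wart must receive an additional treatment". Section 4.7 (30-day visit) and Section 4.8 (60-day visit) likewise state that the next treatment will be given. None of the three mentions the condition of the skin.

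Section 10.3.2.1, rule (c), lists as a stopping criterion: "Scab or crust that is so severe at the 30 day visit that it would preclude additional treatment that day". It is met only when this occurs in more than 2 of the first 20 CellFX subjects, or in "more than 10% of subjects treated after the first 20 subjects". At or below those limits this rule does not stop the study.

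Note 1 of Section 3.2 gives the status of a missed retreatment: "Eligible warts that should be treated and do not receive a retreatment will be considered a protocol deviation". The reason goes on the eCRF, and the subject stays in the study and in ITT. PP is not mentioned there.

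Section 6.4 defines PP by subject. Among other conditions, the subject must have "repeated the treatments per protocol for any warts classified as" unresolved at Day 30 or Day 60. The same section makes ITT the primary efficacy population and modified ITT (every wart treated at least once) the population for primary safety. Section 6.5 adds: "Primary and secondary endpoints will be evaluated for the ITT and PP populations". Section 6.1.1 counts both scabbing and crusting as wound-healing events.

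**The concern.** An unresolved wart with a severe scab or crust at Day 30 falls under two texts that do not fit together. One requires treatment at that visit; the other takes for granted that treatment may be impossible that day. Sites need a single instruction.

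The statistical consequence follows from the population definitions. If the site withholds treatment, that one wart makes the subject fail the PP condition, and all of the subject's 2 to 8 warts leave PP. The reason for the exclusion, a bad scab or crust, is of the same kind as the events in the wound-healing composite. PP membership then depends on the outcome, and the PP wound-healing rate is understated in whichever arm has more such exclusions. At stake is how far the PP safety result can be trusted as support for the primary one.

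**Working it through.** **Textual chain**

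1. Sections 3.2 and 4.7: unresolved at Day 30 means retreat. No exception is stated.
2. Rule (c): a scab or crust at that visit may preclude treatment. Some such cases are tolerated while the study continues.
3. Section 3.2, Note 1: no retreatment means a deviation. The reason is recorded but is given no effect on status.
4. Section 6.4: a subject with any unresolved wart not retreated per protocol fails the PP definition.
5. Sections 6.4 and 6.5: primary endpoints, wound healing included, are also evaluated in PP.

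The chain applies only to a wart that is both unresolved and not retreated. Rule (c) itself covers only scab or crust, and only at the 30-day visit.

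**Size**

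The plan gives no figure for this effect, so there is none to reproduce. What follows is an illustration.

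Inputs from the plan: 150 subjects in total (Section 6.3), taken as 75 per arm; 3 warts per subject; planned wound-healing rates of 37.6% (CellFX) and 43% (cryosurgery); margin 15 points (Section 6.1.1). Assumptions: no other PP exclusions, no loss to follow-up, and rule (c)'s 10% clause applied to the remaining CellFX subjects.

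Largest number tolerated by rule (c): 2 of the first 20, plus 5 of the next 55 (10% of 55 = 5.5, rounded down) = 7 of 75.

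CellFX warts: 75 × 3 = 225. Expected events: 225 × 0.376 = 84.6.

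If k subjects are excluded with an average of e event warts each, the PP rate is (84.6 − k·e) / (225 − 3k).

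- One affected wart each, the other two at the planned rate: e = 1 + 2 × 0.376 = 1.752.
- All three warts affected: e = 3.

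| CellFX subjects excluded | e | PP CellFX rate | Fall from 37.6% |
|---|---|---|---|
| 7 | 1.752 | (84.6 − 12.264)/204 = 35.5% | 2.1 points |
| 7 | 3 | (84.6 − 21)/204 = 31.2% | 6.4 points |
| 2 | 1.752 | (84.6 − 3.504)/219 = 37.0% | 0.6 points |
| 2 | 3 | (84.6 − 6)/219 = 35.9% | 1.7 points |

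These rows assume no exclusions under cryosurgery, so the fall in the CellFX rate is also the shift in the difference.

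Equal worst-case loss in both arms (7 subjects each, all 21 warts with events):

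- Cryosurgery: 225 × 0.43 = 96.75 events; (96.75 − 21)/204 = 37.1%.
- CellFX: 31.2%, as above.
- The difference goes from 37.6 − 43 = −5.4 points to 31.18 − 37.13 = −5.95, or about −6.0 points: a shift of about 0.6 points.

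**The case against.** The strongest reply is that nothing decisive rests on PP, and that stands. A reader might infer that the wound-healing co-primary, or study success, is biased. The documents do not support this: modified ITT keeps every wart treated at least once, Note 1 keeps these subjects in ITT for efficacy, and neither Section 6.1.1 nor Section 6.1.4 ties success to PP. A reader might also treat PP as a confirmatory check, as is often done in non-inferiority trials. Section 6.4 says only that outcomes are also analysed in PP, and Section 6.5 describes its analyses as checks of consistency.

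Other points also have force. Rule (c) is a study-level stopping trigger, not a treatment instruction, and Note 1 already provides for a retreatment that is not given. Section 11.6 requires deviations to be reported even when medically justified, so the label carries no blame; that it would push sites to retreat unhealed skin is conjecture. Rule (c) does not mention ulcers or Day 60, so the contradiction should not be extended to them.

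The size depends heavily on assumptions. The plan expects more wound-healing events under cryosurgery than under CellFX, so loss in the CellFX arm alone is an extreme case. Timing matters too: a wart passed over at Day 30 but treated at Day 60 has its endpoint read 30 days after that later treatment, so the Day-30 scab need not be the measured event. A reader might take this shift in timing as a bias in the primary analysis. But wart-specific timing is part of the endpoint definition, the wart stays in modified ITT, and the documents give no ground for saying which arm would gain.

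What does not stand is that the matter is already settled. The phrase in Note 1 limiting it to eligible warts that ought to be treated could be read as sparing a precluded wart, but no text says so. Section 11.10 allows case-by-case data decisions before lock, which is not a stated rule. Section 6.0 refers to the SAP for detail, but nothing in the text reviewed gives a PP rule that resolves this.

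**Conclusion.** The point holds in a limited form and should be fixed. Sections 3.2 and 4.7 do not fit with rule (c) and must be reconciled; which clinical criterion applies is not for this review to say. The PP definition, read with Note 1, makes exclusion depend on an outcome that the wound-healing endpoint measures.

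The resulting bias is confined to the supportive PP analyses. On the plan's own rates it ranges from 0.6 to 6.4 points in the CellFX rate, against a 15-point margin, when between 2 and 7 CellFX subjects and no cryosurgery subjects are excluded. The top of that range also needs every wart of every excluded subject to have the event. If the worst-case loss is equal in both arms, the difference moves by about 0.6 points. How often retreatment will be withheld, and in which arm, cannot be known from the documents.

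**What to change.** - Reconcile Sections 3.2 and 4.7 with rule (c) so that sites have one instruction, and align Section 4.8 for consistency. The sponsor and the Safety Monitor set the clinical criterion.
- State in Note 1 and Section 6.4 that a retreatment withheld for a documented safety reason does not exclude the subject from the PP analysis of the safety endpoints. It may still be recorded as a deviation.
- Show PP effectiveness with and without these subjects. Keeping subjects who missed an assigned treatment also changes that analysis, and the reader should see by how much.
- Tabulate withheld retreatments by arm and reason, from the eCRF field already planned.

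The cost is wording in four sections, one table and one additional PP effectiveness run. The downside for the sponsor is that the PP safety result may look slightly less favourable. No primary analysis, margin or sample size changes.
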